11.6.2 Laboratory Data

For hematology and biochemistry panels, local laboratory will be used.

Descriptive statistics (n, mean, SD, SEM, median, minimum and maximum) for laboratory parameters will be computed at each scheduled assessment (*Table 14.3.3.1 and Table 14.3.3.2*). If relevant for some parameter, change from baseline will also be tabulated.

Each laboratory value that is outside of the institution's normal range will be identified. The Investigator will be responsible for assessing the clinical significance of laboratory abnormalities. If the Investigator is uncertain about the clinical significance of a laboratory abnormality, he/she will consult with the Sponsor medical monitor.

Laboratory data listings will be presented in two ways:

- Abnormal values (presented within the data summaries) (*Table 14.3.3.3*)
- All laboratory data (presented within the data listings)

The absolute values of each parameter will be summarised at each visit.

In addition, shift tables from baseline will be presented.

If lab results are repeated at the same visit, the repeated result will be used in summaries (instead of the original one) provided the sample was taken within the visit window, otherwise the original result will be used. All results will be listed.

Lab results at unscheduled visits will be included in the listings but will not be summarised.

Serum pregnancy data will be listed only.

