6.2. Premature trial discontinuation

A patient can be withdrawn at any time from the study for the following reasons:

Patient's premature trial discontinuation could occur for the following reasons:

- Investigator's decision;
- An Adverse Event or an intercurrent condition that preclude continuation of treatment;
 - Specifically, an increase ≥ 3.0 x ULN in liver transaminases (AST/SGOT and/or ALT/SGPT) or an increase ≥ 2.0 x ULN in Alkaline phosphatase or in total bilirubin requires close observation with repeating liver enzymes and serum bilirubin tests two times weekly and clinical investigation to understand the etiology of this elevation. Frequency of retesting can decrease to once a month if abnormality stabilizes after this initial two weeks of follow-up and if the patient is asymptomatic. Discontinuation of the study treatment should occur if:
 - ALT or AST > 8 xULN
 - ALT or AST > 5 xULN for more than 2 weeks
 - ALT or AST > 3 xULN and total bilirubin > 2 xULN or INR >1.5
 - ALT or AST > 3 xULN with appearance of fatigue, nausea, vomiting, right upper quadrant pain or tenderness, fever, rash, and/or eosinophilia ($>5\%$).
- Worsening of the RA (according to physician evaluation);
- Major protocol violation;
- Withdrawal of consent;
- Administrative reasons from Sponsor.

A patient who prematurely exits the study will not be replaced.

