3 STUDY DESIGN

3.1 OVERVIEW

This Phase IIa study is a randomized, double blind, placebo controlled, parallel group, multiple dose study on ABX464 in combination with methotrexate (MTX), in patients with moderate to severe active Rheumatoid Arthritis who have inadequate response to MTX or/and to an anti- tumor necrosis factor alpha (TNF α) therapy, or intolerance to anti-TNF α therapy.

Several experimental and clinical endpoints will be assessed to obtain information on preliminary efficacy in patients with moderate to severe active Rheumatoid Arthritis. Although no formal hypothesis will be tested, these endpoints will enable a broader understanding of the mechanism of action and potential for clinical efficacy of ABX464 in Rheumatoid Arthritis. No interim analysis is planned.

Up to 60 patients will be randomized in this study. These patients will be enrolled in approximately 20 sites located in Europe. At the beginning, the first 6 patients will be randomized to receive either ABX464 50mg (n=4) or its matching placebo (n=2). The Data Safety Monitoring Board (DSMB) will review the safety of these first 6 patients dosed for at least 2 weeks. Once the DSMB recommendation is granted, the next patients will be randomized to receive either ABX464 50mg, ABX464 100mg or placebo. Then, a second DSMB meeting will be held after the next 6 patients are randomized to check the tolerability

[figure not shown]
of the 100mg dose. Once the DSMB recommendation is granted, the next patients will be randomized to receive either ABX464 50mg, ABX464 100mg or placebo. The study randomization ratio is 1:1:1.

The recruitment period is between Q2 2019 and Q3 2020, the overall study period is between Q2 2019 and Q1 2021.

Patients will be treated for 12 weeks, followed by a follow-up period (21 days). The total duration of participation in the study will be approximately 15 to 19 weeks from screening to the last study visit (screening and baseline could occur at the same visit). From Baseline / Day 0 onwards, randomized patients will be seen at the investigational site after 1 Week (Day 7), 2 weeks (Day 14), 4 weeks (Day 28), 8 weeks (Day 56) and 12 weeks (Day 84).

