9.2 EXTERNAL DATA

9.2.1 Laboratory Data

Results from Local lab will be entered in CRF for Haematology, Chemistry, Pregnancy (Serum/ urine), Thyroid (for applicable sites only) and ESR (additionally for fibrinogen, troponin I & T, prothrombin time and/or INR, depending upon CSP version they get consented to).

The following table displays the clinical laboratory parameters:

HEMATOLOGY	BIOCHEMISTRY
Hemoglobin	Sodium
Hematocrit	Potassium
WBC	Chloride
Neutrophils	Calcium
Lymphocytes	Phosphate
Monocytes	Glucose
Eosinophils	BUN or urea
Basophils	Creatinine
Platelet count	AST / SGOT
ESR	ALT / SGPT
Prothrombin time and/or INR*	Alkaline phosphatase
Fibrinogen*	GLDH
	LDH
	Lipase
	Total cholesterol
	HDL cholesterol
	LDL cholesterol
	gGT
	Total bilirubin
	Total protein
	Albumin
	CRP
	T3, T4, TSH (for French sites only)
	Troponin I & T*

Tests of TB (Quantiferon TB Gold Plus), HIV (anti-HIV Ab), HCV (anti-HCV Ab), HBV (HBsAg, anti-HBs Ab), anti-HCV Ab, will be performed only at screening. * Except at Week 1 & 2

Reference ranges will be provided by the labs before site initiation and the required parameters will be transcribed onto the Data Management Laboratory Reference Range Form by the CRA. The CRA will provide reference ranges to the DM, who will use them to verify data on CRF. Further information or language translations will be provided by the responsible CRA if required.

A negative or positive result will be counted in the tables under number of positive or number of negative values. For a parameter with only a result in the comment stated that it is inferior to a certain value (< X), all data will be flagged where there is a sign "<" to count how many data are inferior to the detection limit.

No external data transfers are scheduled for this study.

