10.5 POOLING OF SITES

Sites will be pooled for all analyses. There will be no adjustment for centre effect or treatment by centre interaction.

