*This layout also applies to:
Table 14.3.2.3 Listing of Withdrawals Due to Adverse Events (Safety Set)*

ABX464-301

ddMMMyyyy

Table 14.3.3.1 Summary of Laboratory Parameters: Haematology (Safety Set)

		ABX-464 100mg (N=xx)	ABX-464 50mg (N=xx)	Placebo (N=xx)	Total (N=xx)
Haematocrit					
Baseline	N	xx	xx	xx	xx
	Mean	xx.xx	xx.xx	xx.xx	xx.xx
	SD	xx.xx	xx.xx	xx.xx	xx.xx
	SEM	xx.xx	xx.xx	xx.xx	xx.xx
	Median	xx.xx	xx.xx	xx.xx	xx.xx
	Minimum	xx.x	xx.x	xx.x	xx.x
	Maximum	xx.x	xx.x	xx.x	xx.x
Week 1	N	xx	Xx	Xx	Xx
	Mean	xx.xx	xx.xx	xx.xx	xx.xx
	Etc				
Change from baseline to Week 1	N	xx	Xx	Xx	Xx
	Mean	xx.xx	xx.xx	xx.xx	xx.xx
	Etc				
Etc					
Etc					

Source: Listing 16.2.8.1

Path\Filename

Page x/y

Programming note: start each parameter on a new page

This layout also applies to:

Table 14.3.3.2 Summary of Laboratory Parameters: Biochemistry (Safety Set)

ABX464-301

ddMMyyyy

Table 14.3.3.3 Listing of Abnormal Laboratory Values (Safety Set)

Treatment	Patient number	Visit	Laboratory Parameter	Value
xxxxxx	xxx-xxxx	Week x	xxxxxxxxxxxxxxxxxxxxxx	xx.xx
			xxxxxxxxxxxxxxxxxxxxxx	xx.xx
			Etc	
		Etc		
	Etc			
Etc				

Path\filename

Page x/y

ABX464-301

ddMMMyyyy

Table 14.3.4 Vital Signs (Safety Set)

		ABX-464 100mg (N=xx)	ABX-464 50mg (N=xx)	Placebo (N=xx)	Total (N=xx)
Systolic BP (mmHg)					
Baseline	N	xx	xx	xx	xx
	Normal	xx (xx.x %)	xx (xx.x %)	xx (xx.x %)	xx (xx.x %)
	Abnormal NCS	xx (xx.x %)	xx (xx.x %)	xx (xx.x %)	xx (xx.x %)
	Abnormal CS	xx (xx.x %)	xx (xx.x %)	xx (xx.x %)	xx (xx.x %)
	Mean	xx.xx	xx.xx	xx.xx	xx.xx
	SD	xx.xx	xx.xx	xx.xx	xx.xx
	SEM	xx.xx	xx.xx	xx.xx	xx.xx
	Median	xx.xx	xx.xx	xx.xx	xx.xx
	Minimum	xx.x	xx.x	xx.x	xx.x
	Maximum	xx.x	xx.x	xx.x	xx.x
Week 1	N	xx	xx	xx	xx
	Normal	xx (xx.x %)	xx (xx.x %)	xx (xx.x %)	xx (xx.x %)
	Etc				

Etc

Etc

The denominator for each percentage is the number of non-missing observations within the column.
NCS = Not Clinically Significant; CS = Clinically Significant

Source: Listing 16.4.9
Path\Filename

Page x/y

Programmer's Note: List of variables consists of body temperature, weight, systolic and diastolic blood pressure, heart rate and respiratory rate.

ABX464-301

ddMMMyyyy

Table 14.3.5 Shift Table of Physical Examination (Safety Set)

		ABX-464 100mg (N=xx)		ABX-464 50mg (N=xx)		Placebo (N=xx)		Total (N=xx)	
		normal	abnormal	normal	abnormal	normal	abnormal	normal	abnormal
Eyes									
Baseline	N	xx (xx.x %)	xx (xx.x %)	xx (xx.x %)	xx (xx.x %)	xx (xx.x %)	xx (xx.x %)	xx (xx.x %)	xx (xx.x %)

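### Liver tests from local laboratories are summarised only as pooled absolute values at scheduled visits, so no planned output counts patients per arm at the protocol's ULN-based liver limits

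*SAP*

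**What the plan says.** **Source and pooling.** SAP 11.6.2: "For hematology and biochemistry panels, local laboratory will be used". SAP 3.1: "These patients will be enrolled in approximately 20 sites located in Europe". SAP 10.5: "Sites will be pooled for all analyses".

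**Scale.** SAP 11.6.2: "The absolute values of each parameter will be summarised at each visit". Tables 14.3.3.1 and 14.3.3.2 give n, mean, SD, SEM, median, minimum and maximum, and their shared shell adds change from baseline.

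**Reference ranges.** SAP 9.2.1: "The CRA will provide reference ranges to the DM, who will use them to verify data on CRF". SAP 11.6.2 and Protocol 5.3.5 also use the institution's range to identify values outside it.

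**What the summaries leave out.** Under SAP 11.6.2, unscheduled results are listed but not summarised, and a repeat taken within the visit window replaces the original value.

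**Listings.** Table 14.3.3.3 (abnormal values) has columns for treatment, patient, visit, parameter and value. Listing 16.2.8.2 takes the layout of 16.2.8.1: result, unit and investigator's interpretation. Neither has a reference range or a multiple of ULN.

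**Liver limits in Protocol 6.2.** Close observation, with liver tests repeated twice weekly, applies at ALT or AST of at least 3 x ULN, or at ALP or total bilirubin of at least 2 x ULN. The stopping criteria are "ALT or AST > 8 xULN"; above 5 x ULN for more than 2 weeks; above 3 x ULN with bilirubin above 2 x ULN or INR above 1.5; and above 3 x ULN with listed symptoms or eosinophilia.

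**The concern.** The protocol manages liver safety on one scale and the SAP reports it on another. Safety is the primary objective. Protocol 1.2.5.1 names the liver as a main target organ in animals, describes toxic effects in minipigs appearing shortly before the end of the third month of dosing, and says that a specific liver monitoring plan is in place. This trial doses for 12 weeks, yet no planned output reports, by arm, what that monitoring found.

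A by-arm count matters more because every patient takes methotrexate. The methotrexate product information in Protocol Appendix 5 reports temporary transaminase rises to two or three times ULN in 13 to 20% of patients. Background rises near the 3 x limit are therefore plausible in every arm, and a drug effect would have to be judged against placebo at the same limits.

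**Working it through.** **1. The plan's own safety figures.** SAP 3.5 gives an 88% chance of seeing at least one event of rate 1:10 in 20 patients, and 87% for rate 1:20 in 40 patients.

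- 1 − 0.90^20 = 0.878
- 1 − 0.95^40 = 0.871

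Both reproduce. They describe the chance that an event occurs, so they help the reader only if the event is then counted.

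**2. Protocol limit against planned output.**

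| Protocol 6.2 limit | Planned output counting it by arm |
|---|---|
| ALT or AST ≥3 x ULN | none |
| ALP ≥2 x ULN; bilirubin ≥2 x ULN | none |
| ALT or AST >8 x ULN | none |
| ALT or AST >5 x ULN for more than 2 weeks | none |
| ALT or AST >3 x ULN with bilirubin >2 x ULN or INR >1.5 | none |
| ALT or AST >3 x ULN with symptoms or eosinophilia | none |

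An in-range or out-of-range flag treats 1.1 x and 7 x ULN alike. SAP 11.6.2 promises laboratory shift tables, but none is in the table list or shells, and a normal/abnormal shift would not separate 3, 5 and 8 x ULN in any case.

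**3. Why a raw value cannot stand in (illustration).** Assume local ALT ULNs of 35 to 55 U/L. The documents give no such figures.

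| Assumed ULN (U/L) | 3 x | 5 x | 8 x | 120 U/L as multiple |
|---|---|---|---|---|
| 35 | 105 | 175 | 280 | 120/35 = 3.43 |
| 45 | 135 | 225 | 360 | 120/45 = 2.67 |
| 55 | 165 | 275 | 440 | 120/55 = 2.18 |

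The same printed value meets the 3 x limit at one laboratory and not at the other two.

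**4. Where the repeat tests fall.** Scheduled post-baseline visits are Days 7, 14, 28, 56, 84 and 105, each ± 2 days. Assume repeats at alternating 3- and 4-day gaps for two weeks:

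- rise found on Day 7: tests on Days 10, 14, 17 and 21, of which one (Day 14) is in a window;
- found on Day 14: Days 17, 21, 24 and 28, one (Day 28) in a window;
- found on Day 28: Days 31, 35, 38 and 42, none in a window;
- found on Day 56: Days 59, 63, 66 and 70, none in a window.

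Most repeats are therefore unscheduled and drop out of the summaries. These are the results that bear on the two-week criterion.

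**5. Expected background (assumption).** If the 13 to 20% rate applied here, 20 × 0.13 = 2.6 to 20 × 0.20 = 4.0 patients per arm would have such rises. The chance of at least one in an arm would be 1 − 0.87^20 = 0.94 to 1 − 0.80^20 = 0.99.

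**The case against.** **Other outputs carry liver information.** Protocol 6.2 places these limits under discontinuation for an adverse event or intercurrent condition. The SAP has by-arm tables of TEAEs leading to discontinuation (14.3.1.4.1 and .2), grade 3 or 4 TEAEs (14.3.1.5.1 and .2) and reasons for withdrawal (14.1.3), plus a listing of withdrawals due to adverse events. SAP 11.6.1 plans a review of individual values, and there are at most 60 patients. This stands in part: a reader might infer that the report could show no liver signal by arm, and the documents do not support that. But under Protocol 7.3.1 a laboratory value becomes an adverse event only if the investigator judges it clinically significant, and none of these tables counts patients at the limits.

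**Local ranges are used for more than CRF checks.** Correct: they also decide which values are flagged as out of range. Only the descriptive tables are on the raw scale.

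**Raw pooling need not bias the comparison.** Also correct. Allocation is randomised, and the shell includes change from baseline, which largely removes fixed level differences if a patient stays with one laboratory. Differences between laboratories would then add noise, not systematic bias between arms. Neither point yields a count at a limit. The maximum in Table 14.3.3.2 shows the highest scheduled raw value in an arm, but not its multiple. No unit conversion is described; that is silence, not evidence that none will be done.

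**Layouts are provisional.** SAP 15 lets the programmer change them for completeness and clarity. That does not commit anyone to the missing scale or to summarising unscheduled tests.

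**Clinical experience.** Protocol 1.2.5.1 also says that no signs of hepatotoxicity were seen in treated patients. The point is about reporting and predicts no liver signal.

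**Conclusion.** The concern holds for liver tests, as a gap in the planned outputs. None of the six rows in the comparison of limits with outputs has a by-arm count, no listing lets a reader rebuild a multiple of ULN, and most repeat tests would fall outside the summaries. The gap exists as planned and can be closed, because the local ranges are collected.

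Three wider readings are not supported. It does not extend to all laboratory parameters, since the protocol limits cited are for the liver. Not every liver criterion is on the ULN scale: INR, symptoms and eosinophilia are not. And no trial result is shown to be wrong; the stated detection probabilities reproduce.

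The size rests on assumptions. The 35 to 55 U/L range is illustrative, the 13 to 20% background rate comes from the methotrexate product information and may not apply here, and the repeat-test days assume even spacing. The core needs only that local ULNs can differ, which collecting reference ranges from the local laboratories already allows for. No view is taken on the clinical limits themselves. This is an inexpensive improvement to a trial whose primary objective is safety, best made before database lock.

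**What to change.** 1. Load each site's ULN into the analysis data and derive value/ULN for ALT, AST, ALP and total bilirubin.
2. Add one by-arm Safety Set table of patients reaching each limit as written in Protocol 6.2 at any post-baseline test. Include unscheduled tests and original values later repeated. Rows:
   - ALT or AST ≥3 x ULN
   - ALP ≥2 x ULN
   - total bilirubin ≥2 x ULN
   - ALT or AST >8 x ULN
   - ALT or AST >5 x ULN, with a separate row for >5 x ULN lasting more than 2 weeks
   - ALT or AST >3 x ULN with either bilirubin >2 x ULN or INR >1.5
3. List the cases of ALT or AST >3 x ULN with the protocol's symptoms or eosinophilia.
4. Add unit, reference range and x ULN to Table 14.3.3.3, and reference range and x ULN to Listing 16.2.8.2.
5. State in a footnote how many patients had an evaluable INR. The laboratory table allows prothrombin time and/or INR and omits it at Weeks 1 and 2, and SAP 9.2.1 makes its collection depend on the protocol version consented to.

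The cost is entering ranges already collected, one extra table, a short case listing and a few listing columns. No clinical rule and no data collection changes. SAP 1.1 says recruitment was still ongoing when the plan was written, so there was time to add this before lock.

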11.6.3 Vital Signs

Vital signs will be summarized by using descriptive statistics (n, mean, SD, SEM, median, minimum and maximum) (*Table 14.3.4*). Number of patients with at least one abnormal value will be tabulated (counts and percentages) for each parameter in summary shift tables, by group and dose.

Measurements of vital signs will be done at each visit (Blood pressure, Heart Rate, Body temperature).

The investigator should ensure that each parameter outside the normal range is assessed for clinical significance. For any deviation assessed clinically significant, the investigator has to document the change as an AE in the CRF.

In addition, it is at the discretion of the investigator to document any change or trend over time in vital signs as an AE if he considers the change to be clinically significant, even if the absolute value is within the alert limit or reference range.

11.6.4 Physical Examination

A routine physical examination (including body weight) will be done at each study visit. Physical examinations will cover eyes, ears, nose, throat, lungs/thorax, heart/cardiovascular system, abdomen, skin and mucosae, nervous system, lymph nodes, musculo-skeletal system, and, if applicable, others. Any new clinically relevant finding compared to baseline must be documented as adverse event.

Shift tables will be presented showing changes from baseline to each visit for normal / abnormal physical examination results (*Table 14.3.5*).

11.6.5 Electrocardiogram

Electrocardiograms will be performed at Screening, Baseline / Day 0, Week 8 / Day 56 and at the EOS visit (in case of premature discontinuation only). At least a 12-lead ECG with recordings of at least 6 action potentials in lead II (paper speed 25mm/s, amplitude 10mm/mV) will be measured at a resting position. Resting ECG should be performed before any examinations.

All abnormal findings must be documented in the CRF. Any clinically relevant findings compared to ECG done at Day 0 / Baseline must be documented as adverse events.

The absolute values of PR, QRS, QT and QTc will be summarised at each visit done (screening, baseline, week 8 and EOS) (*Table 14.3.6*).

The number and percentage of the patients with Normal / Abnormal NCS / Abnormal CS ECG results will be summarised.

11.7 STUDY DRUG EXPOSURE AND COMPLIANCE

Treatment exposure (ABX464 50mg, 100mg or placebo) and compliance (yes/no) will be summarised for the FAS (*Table 14.3.7*).

11.8 PRIOR AND CONCOMITANT MEDICATION

All medications taken by patients on entry to the study or during the study will be recorded in the CRF. Medications will be classified using the version of the World Health Organisation Drug Dictionary (WHODD) coding dictionary defined in the Data Management Plan. The Anatomical Therapeutic Chemical (ATC) Classification and WHO-DRUG PT will be used to list and summarise the data.

If required by client, conmeds can be summarised at 3 levels: ATC levels 1 and 2 and preferred term.

Prior medications are defined as medication that started and stopped before Day 1. Only medications where the stop date is prior to Day 1 will be considered prior. If the stop date is unknown or incomplete and the medications cannot definitely be considered as stopped prior to Day 1 then the medications will be considered as concomitant medications at randomisation or change in concomitant medication, depending on the start date.

Concomitant medications at randomisation are defined as medications that started before Day 1 and either stopped on Day 1 or continued into the study. Partial start dates where the medication cannot

definitely be considered as starting prior to Day 1 will lead to a categorisation of the medications as having started on or after dosing.

Change in concomitant medication is defined as medication that started on or after Day 1. If the medication start or stop dates are partial then the rules for prior and concomitant medication, detailed above will be observed prior to assigning a category.

The number (%) of patients reporting the use of any prior medications and the number (%) of patients taking each drug by ATC classification and PT will be summarised using the FAS (Table 14.3.8). This table will be repeated for concomitant medications at randomisation (Table 14.3.9.1) and for change in concomitant medication (Table 14.3.9.2)

Mandatory concomitant treatments are the followings:

- MTX \geq 10 mg/week, at stable dose, throughout the study;
- Folic acid \geq 10 mg/week post MTX dose, to minimize MTX toxicity.

Allowed Concomitant Medications are the followings:

- Corticosteroids at stable dose of prednisone and prednisone equivalent \leq 10 mg/day during the study;
- Non-steroidal anti-inflammatory drugs (NSAIDs) at stable dose during the study;
- Antalgics including class III at stable dose during the study;
- Other non-rheumatologic medications.

Potential other concomitant medications (not indicated for rheumatoid arthritis) should be kept at constant dose during the course of the study and properly reported in the medical file of the patient and the eCRF.

Prohibited concurrent medications are the followings:

- Any non-anti-TNF α biological or targeted DMARDs: IL-6 antagonists, JAK inhibitors, CTLA-4Fc Chimera, rituximab;
- Any immunosuppressive drugs;
- Vaccination with live components during the study and up to 8 Weeks after the last dosing;
- Drugs that could interact with ABX464 should be avoided especially the CYP1A2 substrates. The following CYP1A2 substrates with a narrow therapeutic margin are prohibited during the whole course of the study (rifampicin, clozapine, theophylline, ropinirole, warfarin and methadone). In case of concomitant treatment with ondansetron, the maximal daily dose must be limited to 8 mg;
- Use of any investigational or non-registered product within 3 months preceding baseline.

